8.5 Stopping Criteria

The study will be halted, and the risk to other subjects evaluated, prior to a decision as to whether to terminate the study if any of the following criteria are met:

- The occurrence of an SAE considered at least possibly related to the IMP administration in 1 subject.
- The occurrence of severe, non-serious AEs considered at least possibly related to the IMP administration in 2 subjects in any treatment period.

Relatedness will be determined by the investigator and/ or sponsor. If the study is halted, a temporary halt will be submitted to the Medicines and Healthcare products Regulatory Agency (MHRA) and ethics committee (EC) in the form of a substantial amendment. The study will not be resumed until a further substantial amendment to resume the study is submitted and approved by MHRA and EC.

8.6 Study Termination

After the start of protocol activities but prior to the commencement of dosing, the study may be terminated by the sponsor and investigator without consultation with the MHRA and EC. The end of the trial must be notified to the MHRA and EC immediately and at the latest within 15 days after the study is halted, clearly explaining the reasons. A description of follow-up measures taken for safety reasons if applicable, should also be provided.

If the study is abandoned prior to commencement of any protocol activities, the investigator or sponsor must notify the EC and MHRA by letter outlining the reasons for abandonment of the trial.

Once exposure to IMP dosing has begun, the study will be completed as planned unless the following criteria are satisfied that require temporary suspension or early termination of the study:

• The occurrence of SAEs (s), as defined in Section 8.5, if considered to be related to the IMP, as defined in Section 14.2.

- New information regarding the safety of the IMP that indicates a change in the risk/benefit profile for the compound, such that the risk/benefit is no longer acceptable for subjects participating in the study.
- Significant violation of Good Clinical Practice (GCP) that compromises the ability to achieve the primary study objectives or compromises subject safety.

If any of the above occurs, the study may be terminated if careful review of the overall risk/benefit analysis described in Section 6.4 demonstrates that the assumptions have changed and that the overall balance is no longer acceptable. In these circumstances termination can only take place with the agreement of the investigator and sponsor. The MHRA and EC will be informed of study termination.

If it becomes necessary to consider termination of the study after dosing has begun, dosing may be suspended pending discussion between the investigator and sponsor. Dosing will be stopped immediately on safety grounds.

The study may be terminated or suspended at the request of the MHRA or EC.

8.7 Treatment Allocation

This is an open-label, non-randomised study, therefore, a randomisation schedule will not be produced. A treatment allocation list will be produced prior to dosing with IMP, which will dictate the order in which the treatments should be administered to each subject. The treatment allocation list will be retained in the investigator site file.

8.7.1 Subject Numbers

Part 1

Subject numbers will be allocated on the morning of IMP dosing according to the code 001 to 040 using the lowest number available. If required, replacement subjects will be allocated subject numbers 901 to 940, where the last 2 digits are the same as those of the original subject (eg if Subject 005 withdraws, the replacement will have Subject Number 905 and will receive the reference treatment, as well as IMP/NIMP for at least one treatment period not already received by the replaced subject).

Part 2

Subject numbers will be allocated on the morning of IMP dosing according to the code 201 to 238 using the lowest number available. If required, replacement subjects will be allocated subject numbers 801 to 838 where the last 2 digits are the same as those of the original subject (eg if Subject 205 withdraws, the replacement will have Subject Number 805 and will receive the reference treatment (Period 1), as well as the IMP/NIMP for Period 2.

8.7.2 Blinding

This is an open-label, non-randomised study and therefore blinding is not required.

9 Selection of Subjects

Quotient Sciences must have a full medical history from each subject's general practitioner within the last 12 months, prior to enrolment in the study.

Subjects will be recruited from the Quotient Sciences panel or by direct advertising to the public.

Before subjects are admitted to the clinic, The Over Volunteering Prevention System (TOPS) will be checked to ensure that each subject has not participated in a study at another site within at least 3 months of the dosing date.

9.1 Informed Consent

Subjects will be provided with a written explanation of the study at least the day before the screening visit. A physician or nurse will explain to each subject the nature of the study, its purpose, expected duration and the benefits and risks involved in study participation. Subjects will be informed that, for safety reasons, brief details of their involvement in the study may be revealed to other units and companies that carry out clinical studies in the local area. Subjects will then be given the opportunity to ask questions and will be informed of their right to withdraw from the study without prejudice. After this explanation and before entering the study, the subject will voluntarily sign an informed consent form (ICF).

9.2 Inclusion Criteria

- 1. Healthy males
- 2. Age 18 to 55 years
- 3. Good state of health (mentally and physically) as indicated by a comprehensive clinical assessment (detailed medical history and a complete physical examination), ECG and laboratory investigations (haematology, clinical chemistry and urinalysis)
- 4. Body weight ≥50 kg
- 5. Body mass index of 18.0 to 32.0 kg/m² or, if outside the range, considered not clinically significant by the investigator
- 6. Must be willing and able to communicate and participate in the whole study
- 7. Must provide written informed consent
- 8. Must adhere to the contraception requirements as defined in Section 9.4)

Inclusion criteria 3 from the list above will be re-assessed at the Period 1 admission.

9.3 Exclusion Criteria

- Subjects who previously participated in any other investigational study drug trial in which receipt of an investigational study drug occurred within 90 days prior to dosing (subjects who have previously received KD025 in Part 1 at least 90 days prior to dosing in Part 2 are eligible to participate).
- 2. Subjects who are study site employees, or immediate family members of a study site or sponsor employee
- 3. Subjects with pregnant partners
- 4. History of any drug or alcohol abuse in the past 2 years
- 5. Regular alcohol consumption in males >21 units per week (1 unit = ½ pint beer, or a 25 mL shot of 40% spirit, 1.5 to 2 units = 125 mL glass of wine, depending on type)
- 6. Current smokers and those who have smoked within the last 12 months. A breath carbon monoxide reading of greater than 10 ppm at screening and admission
- 7. Current users of e-cigarettes and nicotine replacement products and those who have used these products within the last 12 months
- 8. Subjects who do not have suitable veins for multiple venepunctures/cannulation as assessed by the investigator at screening

- 9. Clinically significant abnormal biochemistry, haematology or urinalysis as judged by the investigator (laboratory parameters are listed in Appendix 1)
- 10. Positive drugs of abuse test result (drugs of abuse tests are listed in Appendix 1) or alcohol breath test at screening and admission
- 11. Positive hepatitis B surface antigen (HBsAg), hepatitis C virus antibody (HCV Ab) or human immunodeficiency virus (HIV) results
- 12. Evidence of renal impairment at screening, as indicated by an estimated creatinine clearance (CLcr) of <80 mL/min using the Cockcroft-Gault equation
- 13. History of clinically significant cardiovascular, renal, hepatic, chronic respiratory or gastrointestinal disease, neurological or psychiatric disorder, as judged by the investigator
- 14. Subject has a history or presence of any of the following:
 - Active gastrointestinal disease requiring therapy
 - Hepatic disease and/or ALT or AST > ULN
 - Renal disease and/or serum creatinine > ULN
 - Other condition known to interfere with the absorption, distribution, metabolism or excretion of drugs
- 15. Subjects with a history of cholecystectomy or gall stones
- 16. Subject has QT interval corrected using Fridericia's formula (QTcF) intervals >450 msec at screening or admission
- 17. Serious adverse reaction or serious hypersensitivity to any drug or the formulation excipients; including intolerance to itraconazole, rabeprazole, rifampicin and omeprazole.
- 18. Presence or history of clinically significant allergy requiring treatment, as judged by the investigator. Hayfever is allowed unless it is active
- 19. Donation or loss of greater than 400 mL of blood within the previous 3 months
- 20. Subjects who are taking, or have taken, any prescribed or over-the-counter drug (other than 4 g per day paracetamol) or herbal remedies in the 14 days before IMP administration (See Section 11.4). Exceptions may apply on a case by case basis, if considered not to interfere with the objectives of the study, as agreed by the principal investigator (PI) and sponsor's medical monitor.
- 21. Failure to satisfy the investigator of fitness to participate for any other reason

Exclusion criteria 6, 9, 10, 14, 16, 18, 20 and 21 from the list above will be re-assessed at admission/pre-dose, as applicable.

Healthy subjects who do not meet the inclusion/exclusion criteria for a study should not be enrolled into the study without exception.

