6.3 Population Rationale

The European Medicines Agency (EMA) propose to include subjects in the age group 18 to 55 years with normal weight who are non smokers without a history of alcohol or drug abuse. The latter criteria are proposed to avoid interaction on drug metabolism and to avoid non compliance. In order to avoid any interaction with other medication, no co medication will be allowed.

As this is a Phase I study assessing the bioavailability, PK and safety of KD025, the most relevant population is healthy volunteers, as recommended by the FDA [27] and the EMA guidelines [28].

The purpose of this study is to show a difference between the applied conditions, and therefore it is an advantage to enrol a relatively homogeneous population and to minimise variability. Healthy male subjects, aged 18 to 55 years, will be therefore be enrolled.

Formal rat and rabbit embryo-foetal developmental toxicology studies with KD025 demonstrated potential for embryo-foetal toxicity and/or malformations at clinically relevant exposures. Therefore subjects with pregnant partners will be excluded from this study.

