8.3 Subject Withdrawal

If a subject wishes to leave the study at any time, they will be permitted to do so. Every reasonable effort will be made by Quotient Sciences to complete a final assessment/discharge procedures. Quotient Sciences will advise the sponsor of the withdrawal of any subject from the study.

Early withdrawal is defined as the date of the decision to withdraw the subject from the study. Subject completion is defined as the date of the last procedure conducted or last contact (ie, phone call) for that subject.

If a subject requests to leave the clinical unit earlier than the planned discharge time eg due to unforeseen personal circumstances, but aims to return to the unit to complete the study, this will be documented as a subject self-discharge and a protocol deviation. The subject must complete the planned assessments/discharge procedures before discharge from the clinic and will return for the next study period/assessments, as planned.

Subjects will be withdrawn from the study drugs for the following reasons:

- Experiencing a serious or severe AE including but not limited to:
 - corrected QT (QTc) interval of >500 msec or increase in QTc interval of >60 msec from baseline (confirmed following a repeat ECG [mean of triplicate assessments, as applicable])
 - ALT concentration >3 × the upper limit of the reference range
- Termination of the study
- Upon the subject's request (withdrawal of consent)
- Significant deviation from the protocol
- Concurrent illness or requirement for prohibited medication
- At the discretion of the investigator/sponsor

For the purpose of withdrawal criteria in Parts 1 and 2, baseline will be considered as the Period 1 admission/pre-dose measurement; for QTc withdrawal criteria, baseline will be considered as the mean value of the triplicate pre-dose Day 1 (Period 1) ECG measurement.

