9.5 Pregnancy

Subjects will be instructed that if their partner become pregnant during the study this should be reported to the investigator. The investigator should also be notified of pregnancy occurring during the study but confirmed after completion of the study. In the event that a subject's partner is subsequently found to be pregnant after the subject is included in the study, then consent will be sought from the partner and, if granted, any pregnancy will be followed and the status of mother and/or child will be reported to the sponsor after delivery.

A pregnancy notification form and follow-up will be completed.

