10.2 Admission and Pre-dose Procedures

The identity of the subjects will be confirmed at admission and pre-dose.

In addition, the ongoing eligibility of subjects will be re-assessed at admission/pre-dose, as described in Sections 9.2 and 9.3.

Reserve subjects for the first dose occasion, in any group, will not require admission procedures to be repeated, if dosing is within 2 days.

Part 1: subjects will be admitted to the clinical unit on the morning before IMP administration (Day -1) for Periods 1, 2 and 4, and on the evening before IMP administration (Day -1) for Period 3.

Part 2: subjects will be admitted to the clinical unit on the evening before IMP administration (Day -1) for both periods.

The admission and pre-dose procedures are presented in Appendix 2 and Appendix 3

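### Partner pregnancy (exclusion 3) can arise after screening but is not re-checked at admission, and the protocol does not state that KD025 stops once it is known

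*Protocol*

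**What the plan says.** - **Reason for the exclusion.** Protocol 6.3 cites rat and rabbit studies showing potential embryo-foetal toxicity or malformations at clinically relevant exposures, and concludes: "Therefore subjects with pregnant partners will be excluded from this study". Exclusion 3 in 9.3 carries this out. Section 9.3 also states: "Healthy subjects who do not meet the inclusion/exclusion criteria for a study should not be enrolled into the study without exception".
- **What is re-checked.** Section 9.3: "Exclusion criteria 6, 9, 10, 14, 16, 18, 20 and 21 from the list above will be re-assessed at admission/pre-dose, as applicable". Section 9.2 adds only inclusion 3 (general health), at Period 1 admission. Section 10.2 adds no criterion; it says "the ongoing eligibility of subjects will be re-assessed at admission/pre-dose, as described in Sections 9.2 and 9.3".
- **Partner found pregnant later.** Section 9.5 relies on the subject: "Subjects will be instructed that if their partner become pregnant during the study this should be reported to the investigator". If a "partner is subsequently found to be pregnant after the subject is included in the study, then consent will be sought from the partner", and the pregnancy is followed and reported. Further dosing is not mentioned.
- **Withdrawal.** The list in 8.3 opens "Subjects will be withdrawn from the study drugs for the following reasons". It does not name partner pregnancy; its last entry is "At the discretion of the investigator/sponsor".
- **Protection.** Section 9.4 requires a condom plus an effective method where the partner is of child-bearing potential. Section 9.4.1 calls exposure through ejaculate a significant risk, names pregnant partners, and asks all subjects to use a condom until 90 days after discharge.

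**The concern.** Exclusion 3 depends on a fact that can change between screening and dosing, and between one dosing period and the next. Several other changeable criteria (laboratory results, QTcF, medication, drug screen) are on the re-assessment list; this one is not. Followed literally, the admission procedure never asks the question again after screening.

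The protocol requires condoms of every subject and still excludes men with pregnant partners at entry. It therefore did not treat condoms alone as sufficient reason to dose a man whose partner is known to be pregnant, and that reasoning is the same in Period 4 as in Period 1. Subjects gain no benefit from taking part (6.4.3), so no therapeutic interest weighs against stopping. At stake is avoidable exposure of a third party who is not in the trial.

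**Working it through.** There is no plan figure to reproduce. The check is a comparison of sections, followed by simple counts from the schedule.

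**1. Is exclusion 3 re-checked anywhere?** The exclusions re-assessed are 6, 9, 10, 14, 16, 18, 20 and 21; 3 is absent. The only inclusion re-assessed is 3; inclusion 8 (contraception) is not. Section 8.1 describes confirmation of eligibility at admission for each period, but 10.2 ties that to 9.2 and 9.3. The flow charts (Appendices 2 and 3) show no partner-pregnancy question. They do schedule medical history at admission, and SAP 7.6 describes it as an update.

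**2. Does exclusion 3 still apply before first dose?** Yes. SAP 3.2.1 counts a subject as enrolled once he has qualified and has a subject number, and SAP 5.3 allocates that number on the morning of first dosing. A known pregnancy bars him until then. What is missing is the question. Earliest screening to admission is Day -28 to Day -1: 28 - 1 = 27 days.

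**3. What dosing remains after first dose?** Part 1 gives KD025 in four periods, so 4 - 1 = 3 later dosing days. Part 2 has two BID days, so 2 - 1 = 1. Taking minimum washouts from last dose to next NIMP start, as the Period 1 pattern implies (KD025 on day 1, itraconazole on day 3):

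| Step | Study day |
|---|---|
| Part 1, Period 1 KD025 | 1 |
| Itraconazole days 3 to 11; KD025 on its 8th day | 10 |
| 11 + 8 = 19, rabeprazole starts; KD025 on its 4th day | 22 |
| 22 + 4 = 26, rifampicin starts; KD025 on the 10th day | 35 |
| Part 2, omeprazole starts day 3; KD025 on its 4th day | 6 |

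First to last dosing day is 35 - 1 = 34 days in Part 1 (36 if the 8- and 4-day washouts mean full dose-free days) and 6 - 1 = 5 days in Part 2. Extended washouts lengthen both; no length is given.

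**4. What staff contact falls between periods?** Part 1 outpatient visits (10.3.4) are on Period 3 Day -3 and Period 4 Days -9 and -5, which are study days 19, 26 and 30. The longest stretch without a visit runs from Period 2 discharge (day 12) to day 19, which is 7 days. None of these visits schedules the question.

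**5. How much drug remains at discharge?** Subjects stay until 48 h after the morning dose (8.1). Section 5.3.2 gives a typical half-life of 4 to 8 h. Fraction remaining = 0.5^(hours / half-life).

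| Dose | Hours in clinic | Half-life 8 h | Half-life 4 h |
|---|---|---|---|
| Part 1 single dose | 48 | 0.5^6 = 1.6% | 0.5^12 = 0.02% |
| Part 2 evening dose | 48 - 12 = 36 | 0.5^4.5 = 4.4% | 0.5^9 = 0.2% |

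These are plasma figures. Section 5.3.2 mentions a few half-lives above 8 h, and itraconazole may lengthen it in Period 2.

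**The case against.** The strongest reply is that the plan already covers this case in substance. A reported pregnancy goes to the investigator, who also re-assesses exclusion 21 (general fitness to participate) and can withdraw a subject at discretion under 8.3. Section 6.3 bars these men without a time limit. Section 9.4.1 prescribes the condom with pregnant partners expressly in mind. Confinement and a short half-life limit what any later dose adds. The proposed question would still be self-report.

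Most of this stands, and it rules out two stronger readings that a reader might infer:

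- **That such a man passes every listed re-check and would simply be re-dosed.** The documents do not support this. Exclusion 21 is on the list and 8.3 permits withdrawal, so the outcome is a judgement.
- **That 34 days in Part 1 measures unprotected exposure.** It does not. It is a calendar interval that includes residential stays, long stretches after a single dose has largely cleared, and outpatient contacts on days 19, 26 and 30. Condoms are required throughout.

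A gap in handling contraception non-adherence should not be inferred either: that is a protocol deviation, with a route to withdrawal through 17.2 and 8.3.

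Two things remain. No procedure prompts the question, and discretion is weaker than the rules written for lesser matters: a positive alcohol breath test bars dosing at that admission (14.5.4), and carbon monoxide above 10 ppm excludes the subject (14.5.5). A direct question at admission is also a stronger prompt than a standing instruction to report.

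**Conclusion.** The point holds as a minor safety improvement. A changeable exclusion is left off the re-assessment list, so no check is scheduled for up to 27 days before first dose or before up to three later KD025 periods in Part 1 and one in Part 2. The missing dosing rule is the weaker half, because investigator discretion can already supply the answer.

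The documents give no pregnancy rate, so no expected number of events can be stated. The conclusion that residual risk is small rests on condom use being followed, on the typical 4 to 8 h half-life, and on plasma being a fair guide to exposure through ejaculate. The practical gain is limited further because 6.1 already reports preliminary Part 1 results (n=21); it lies mainly in Part 2 and in any Part 1 subjects still to be dosed. The PK conclusions are not affected.

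**What to change.** 1. In 9.3, add exclusion 3 to the criteria re-assessed, and make clear that this applies at each admission in both parts. Ask it with the medical-history update already scheduled there.
2. In 9.5, add one sentence, cross-referenced in 8.3: once a partner pregnancy is known, no further KD025 is given; the subject completes discharge and follow-up, and the existing pregnancy follow-up applies.
3. Leave the self-report instruction and condom requirement unchanged.

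**Cost.** One question per admission (four per subject in Part 1, two in Part 2) and a protocol amendment under 17.1, with re-consent only if the information sheet and consent form change. The stop rule replaces case-by-case judgement and may rarely lose a subject from later periods. The margin is 40 - 34 = 6 subjects in Part 1 and 38 - 34 = 4 in Part 2, plus up to 4 replacements in each part. A replacement is not free: under 8.4 he must repeat Period 1, so another man receives KD025. Part 1 comparisons already completed by the withdrawn subject stay usable, because each has its own pairwise dataset (SAP 6.2). No PK endpoint, sample size or analysis method changes.

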9.4 Contraception

The following contraception requirements are aligned with guidance issued by the Heads of Medicines Agency: Clinical Trials Facilitation Group [29].

Male subjects who are sexually active with a partner of child bearing potential must use, with their partner, a condom plus an approved method of effective contraception from the time of informed consent until 90 days after study discharge.

The following methods are acceptable:

- Combined (oestrogen and progestogen-containing) hormonal contraception associated with inhibition of ovulation:
 - oral

- intravaginal
- transdermal
- Progestogen-only hormonal contraception:
 - oral
 - injectable/implantable
 - intrauterine hormone-releasing system
- Implantable intrauterine device
- Surgical sterilisation (for example, vasectomy or bilateral tubal occlusion)
- Male condom with either female cap or diaphragm (double barrier)

Alternatively, true abstinence is acceptable when it is in line with the subject's preferred and usual lifestyle. If a subject is usually not sexually active but becomes active, they, with their partner, must comply with the contraceptive requirements detailed above.

